1.1. Overview of Disease and Patient Population

1.1.1 Overview of Disease

Multiple myeloma (MM) is the second most common hematological malignancy with approximately 22,000 new cases diagnosed each year in the United States. Prior to the availability of carfilzomib and pomalidomide, MM patients refractory to both lenalidomide and bortezomib had an event free survival of approximately 5 months and an estimated median overall survival of 9 months¹. The median overall survival (OS) has been extended with the use of pomalidomide and carfilzomib to over 15 months². However, all MM patients will eventually become resistant and new mechanisms of action are important to study and develop in order to continue to improve the OS of relapsed and refractory (RR) patients.

1.1.2 Lenalidomide

Lenalidomide (Revlimid®), a thalidomide analogue, is an immunomodulatory agent with antiangiogenic properties. Its mechanism of action remains to be fully characterized. Lenalidomide inhibited the secretion of pro-inflammatory cytokines and increased the secretion of anti-inflammatory cytokines from peripheral blood mononuclear cells. Of cell lines tested, lenalidomide was effective in inhibiting growth of Namalwa cells (a human B cell lymphoma cell line with a deletion of one chromosome 5) but was much less effective in inhibiting growth of KG-1 cells (human myeloblastic cell line, also with a deletion of one chromosome 5) and other cell lines without chromosome 5 deletions. Lenalidomide inhibited the expression of cyclooxygenase-2 (COX-2) but not COX-1 in vitro. Lenalidomide is indicated for the treatment of patients with transfusion-dependent anemia due to Low- or Intermediate-1-risk myelodysplastic syndromes associated with a deletion 5q cytogenetic abnormality with or without additional cytogenetic abnormalities. Lenalidomide in combination with dexamethasone is indicated for the treatment of newly diagnosed multiple myeloma patients and those who have received at least one prior therapy.

1.1.2.1 Clinical Experience in Relapsed Multiple Myeloma

A multicenter, open-label, randomized phase 2 study evaluated 2 doses of lenalidomide for relapsed, refractory multiple myeloma patients. Seventy patients were randomized to receive oral lenalidomide either 30 mg once-daily or 15 mg twice-daily for 21 days of every 28-day cycle. Patients with progressive or stable disease after 2 cycles received dexamethasone.

Analysis showed an increased grade 3/4 myelosuppression in patients receiving 15 mg twice daily as compared to those receiving 30mg daily (41% versus 13%, P= .03). Responses were evaluated according to European Group for Blood and Marrow Transplantation (EBMT) criteria. Overall response rate (complete, partial, or minor) to lenalidomide alone was 25% (24% for once daily and 29% for twice-daily lenalidomide). Median overall survival (OS) in the 30-mg once-daily and twice-daily groups was 28 and 27 months, respectively. Median progression free survival was 7.7 months on once-daily versus 3.9 months on twice-daily lenalidomide (P = 0.2). Dexamethasone was added in 68 patients and 29% responded. Time to first occurrence of clinically significant grade 3 / 4 myelosuppression was shorter in the twice daily group (1.8 vs 5.5 months, P = .05). Significant peripheral neuropathy and deep vein thrombosis each occurred

in only 3%. Lenalidomide was active and well tolerated in relapsed, refractory myeloma, with the 30-mg once-daily regimen providing the basis for future studies as monotherapy and with dexamethasone³.

In a safety and efficacy study of single agent lenalidomide in relapsed and refractory multiple myeloma patients, lenalidomide 30 mg (days 1-21 of 28-day cycle) was given to 222 patients who had relapsed or progressed after 1 or more prior therapies⁴. Sixty-seven percent of patients had received three or more prior therapies, and 45% had received one or more autologous stem cell transplant. Eighty and 43% of patients had received thalidomide and bortezomib based therapies respectively. The median dose of lenalidomide was 25 mg (5-30mg) and the median duration of treatment was 4.2 months (0.06-38). The overall response rate (complete and partial) was 26% with 2% complete response⁴.

Two phase III trials comparing lenalidomide + dexamethasone to single agent dexamethasone in patients with relapsed and/or refractory multiple myeloma were published^{5, 6}. Patients who had received 1-3 prior therapies, and progressed on their last therapy were randomized to receive lenalidomide 25 mg daily on days 1-21, placebo on days 22-28, plus dexamethasone, 40 mg, days 1-4, 9-12, and 17-20 of every 28 day cycle, or placebo daily for 28 days plus dexamethasone, 40 mg, days 1-4, 9-12, 17-20, every 28 days. The responses reported are summarized in Table 1 while the incidence of DVT and pulmonary embolism are summarized in Table 2. Anemia, thrombocytopenia, neutropenia, fatigue, neuropathy, and constipation were observed more often in the lenalidomide + dexamethasone group compared to the dexamethasone only group; however, these events were generally manageable.

Table 1 Response Rates in Phase III Trials of Relapse refractory MM

	Weber et al (NEJM 2007)			Dimopoulos et al (NEJM 2007)		
	Lenalidomide + Dexa (n=177)	Dexa Alone (n=176)	P Value	Lenalidomide + Dexa (n=176)	Dexa Alone (n=175)	P Value
Overall Response Rate (%)	108 (61)	35 (20)	<0.001	106 (60.2)	42 (24)	<0.001
Complete Response	14.1%	0.6%	<0.001	15.9%	3.4%	<0.001
Median TTP (mo.)	11.1	4.7	<0.001	11.3	4.7	<0.001
Median OS (mo.)	29.6	20.2	<0.001	Not Reached	20.6	0.03

Table 2 DVT & PE Risks in Phase III Trials of Relapse refractory MM

	Weber et al	Dimopoulos et al
--	-------------	------------------

	Lenalidomide + Dexamethasone	Dexamethasone Alone	Lenalidomide + Dexamethasone	Dexamethasone Alone
Deep Vein Thrombosis (%)	11.9	3.4	4.0	3.5
Pulmonary Embolism (%)	3.4	0.6	4.4	1.2

The dexamethasone used in the above two studies is considered high dose. A phase III study compared lenalidomide plus high-dose dexamethasone (doses and schedule as described above) to lenalidomide (dose and regimen as above) plus low-dose dexamethasone (40 mg given on days 1, 8, 15, 22 of 28-day cycles) in newly diagnosed multiple myeloma patients. Overall survival at 1 year was 96% for the low-dose dexamethasone compared to 87% for the high-dose dexamethasone ($P=0.0002$). As a result, the trial was stopped and patients on the high-dose therapy were crossed over to the low-dose therapy⁷. Subsequently, most therapies involving dexamethasone use low-dose.

1.1.2.2 Ibrutinib and Multiple Myeloma

Ibrutinib is a Bruton's tyrosine kinase (Btk) inhibitor. Btk is a member of the Tec family of tyrosine kinases, whose activation regulates B-cell development and plays an important role in antibody production and has been shown to be a therapeutic target in MM^{8, 9}. Treatment of myeloma cells directly with ibrutinib results in a modest reduction in cell viability and induction of apoptosis in vitro. In addition, ibrutinib directly inhibits osteoclastic bone resorption, prevents release of multiple osteoclast-derived tumor growth factors, prevents adhesion of MM cells to bone marrow stromal cells (BMSCs), and inhibits migration of SDF-1-induced MM cells^{10,11}. In addition, Ibrutinib has been shown to inhibit BTK-driven NK-kB p65 activity to overcome bortezomib-resistance^{8, 11}. Dysregulation of osteoclast activity plays a critical role in MM pathogenesis. Btk regulates osteoclast differentiation through RANK signaling, and indeed in pre-clinical studies involving MM cells lines, inhibition of Btk decreased OC function. A phase II study of Ibrutinib single agent or in combination with dexamethasone in relapsed or relapsed/refractory MM showed a clinical benefit across all dose levels but the highest activity of 25% at the highest dose of 840 mg with or without 40mg dexamethasone without the occurrence of new safety signals¹². The number of median prior therapies was 4 (range, 2-14), 41% had ≥ 5 prior therapies and 80% had undergone autologous stem cell transplants. Sixty-two percent of patients were refractory to their last line of therapy including 45% to both an immunomodulatory agent and a proteasome inhibitor. Overall, 57% experienced a Grade 3 or higher adverse event. The most commonly reported non-hematologic toxicities (any grade) were diarrhea (51%), fatigue (41%), nausea (35%), dizziness (25%), and muscle spasms (23%). The majority were Grade 1 and 2. Hematologic toxicity of any grade was anemia (29%), thrombocytopenia (23%), and neutropenia (7%) with 16%, 9% and 4% being Grade 3, respectively. There were no clinically meaningful differences among dose levels. At least one dose modification occurred in 22% of patients, with 6 discontinuing due to an adverse event¹².

1.1.2.3 Ibrutinib and Lenalidomide

The combination of Ibrutinib and lenalidomide have been studied in patients with relapsed and refractory lymphoma and chronic lymphocytic leukemia in a phase 1 and 2 clinical trials. The

phase 2 study in mantle cell lymphoma, a B-cell malignancy, as in MM was well tolerated with the most common grade 3-4 adverse events being neutropenia (38%), infection (22%) and cutaneous toxicity. The preclinical study in MM suggest synergism between lenalidomide and ibrutinib in MM¹¹. A phase 1 / 2b clinical trial of Ibrutinib and pomalidomide (a third generation Imid) is currently ongoing (NCT02548962). The anti-myeloma effects of lenalidomide have been previously described and include caspase-8-dependent apoptosis of MM cells, inhibition of angiogenesis, and activation of NK and T effector cells. Both ibrutinib and lenalidomide downregulate IRF4, a master transcriptional factor that mediates myeloma cell survival, and both exert effects on the BM microenvironment with overlapping yet distinct targets that influence MM cell growth and survival. The combination of lenalidomide and ibrutinib is thus an attractive therapeutic strategy not only as a potent anti-MM regimen but also in terms of positively impacting bone disease.

1.1.3 Study Rationale

MM patients refractory to both lenalidomide and bortezomib have an event free survival of approximately 5 months and an estimated median overall survival of 9 months¹. While this has improved with pomalidomide and carfilzomib to a median of 15 months, all MM patients will eventually become resistant and new mechanisms of action are important to study and develop in order to continue to improve the OS of relapsed and refractory (RR) patients. Ibrutinib, a Btk inhibitor, has shown efficacy as a single agent and in combination with dexamethasone. Pre-clinical studies suggest synergism between Ibrutinib and lenalidomide in MM cell lines.

We seek to determine the response in relapse/refractory multiple myeloma patients using Ibrutinib in combination with lenalidomide and dexamethasone with the primary endpoint of determining safety, tolerability and the maximum tolerated dose (MTD), and secondary endpoints of progression-free survival, overall survival, duration of response, and pharmacokinetic and pharmacodynamics of Ibrutinib in combination with lenalidomide and dexamethasone.

1.2. Study Design

This is a single-arm, open label, phase Ib study of Ibrutinib in combination with lenalidomide and dexamethasone in adult (age 18 years and older) patients with relapsed/refractory MM. A dose-escalation will be completed with the primary endpoint of determining safety, tolerability and maximum tolerated dose (MTDs) in a standard 3+3 design over 3 dose levels of 560, 560 and 840 mg of Ibrutinib given orally daily, lenalidomide given at 15 mg, 25 mg and 25 mg orally daily on days 1-21 of a 28-day cycle and dexamethasone 40 mg given orally weekly (patients 75 yrs and older will start with Dexamethasone20 mg) (Table 3 and 4). Patients with GFR 30-60 ml/min will receive lenalidomide 10 mg daily, days 1 – 21 of 28 according to manufacturer's recommendation. A minimum of 6 and a maximum of 18 patients will be recruited in the phase I portion. Upon identification of the MTD for the dose level combination of Ibrutinib and lenalidomide/dexamethasone, a 10-patient expansion cohort will commence. Secondary endpoints of progression-free survival, overall survival, duration of response, and pharmacokinetic and pharmacodynamics of Ibrutinib in combination with lenalidomide and dexamethasone will be assessed.

Please see Section 7 for dexamethasone dose modification guidelines.

Version Date 22-Jan-2024

CONFIDENTIAL

Version # 3.0

Table 3 Dose Level

	Ibrutinib	Lenalidomide	Dexamethasone^a
1 (starting dose)	560 mg	15 mg	40mg
2	560mg	25 mg	40mg
3	840mg	25 mg	40mg

^a The starting dose of dexamethasone will be reduced to 20 mg based on tolerability or if the patient is 75 years or older at the time of registration.

Table 4 Dosing Schedule

Agent	Dose	Route	Days	ReRx
Ibrutinib	assigned at time of registration	Oral	1-28	
Lenalidomide	assigned at time of registration	Oral	1-21	
Dexamethasone	40 mg if age < 75 years old at registration	Oral	1,8,15, 22	Every 28 days
	20 mg if age ≥ 75 years old at registration			

Please see section 7.1 for the definition of Dose Limiting Toxicity (DLT) occurring during combination of lenalidomide, dexamethasone and Ibrutinib.

Determination of Maximum Tolerated Dose (MTD)

The maximum tolerated dose is defined as the highest dose level among those tested where at most 1 out of 6 patients develops a DLT prior to the start of their second cycle of treatment and the next highest dose level is such that 2 or more out of a maximum of 6 patients treated at this dose level developed a DLT prior to the start of their second cycle of treatment.

Enrollment and determination of MTD

A minimum of 2 or a maximum of 6 patients will be accrued to a given dose level. Doses will not be escalated in any individual patient. If none of the first 3 patients treated at a given dose level develops a DLT during the first cycle of treatment, enrollment to the dose level will be closed and enrollment will reopen at next higher dose level. If there are no other higher dose levels to be tested, three additional patients will be enrolled at the current dose level to confirm MTD. If one of the first 3 patients treated at a given dose level develops a DLT during the first cycle of treatment, three additional patients will enroll onto the current dose level. If, at any time in the enrollment of these 3 additional patients, a patient develops a DLT, enrollment will be closed to this dose level. Enrollment will be re-opened to the next lower dose level if fewer than

6 patients have been treated at that dose level. If none of these 3 additional patients develops a DLT during the first cycle of treatment, enrollment to this dose level will be closed and enrollment will reopen at next higher dose level. If there are no other higher dose levels to be tested, this will be considered the MTD.

For this protocol, the patient must return to their registration institution for evaluation and continuation of treatment (at least every 28 ± 3 days) according to the test schedule. Patients who have not had disease progression and have experienced acceptable toxicity will be eligible to continue protocol retreatment at their current dose level until disease progression, unacceptable toxicity, or refusal. Those patients who have not progressed and who have experienced unacceptable toxicity may be eligible to continue protocol retreatment at a lower dose.

Criteria for discontinuation of all protocol therapy include:

- Tumor progression
- Request by the patient to withdraw
- Unacceptable adverse events
- Treatment delay of >4weeks
- Intercurrent illness which would, in the judgment of the investigator, affect assessments of clinical status to a significant degree or require discontinuation of drug
- Non-protocol chemotherapy, or an experimental drug during the trial

Patients who discontinue treatment for any of the above reasons will go to survival follow-up. Once a patient has entered the survival follow-up phase of the trial, his/her therapy is at the discretion of the treating physician. The sponsor would like to collect that information, if the patient agrees.

Patients who discontinue treatment due to toxicity should be monitored until resolution or stabilization of adverse event.

Expansion cohort

Once the MTD has been established or determined, 10 additional patients will be treated at the MTD. The total number of patients to be enrolled in the study will be 28.

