	
 • Hemoglobin level ≥ 8 g/dL, independent of transfusion support. 
11. Biochemical values must be within the following limits within 7 days prior to registration
 
 • Alanine aminotransferase (ALT) and aspartate aminotransferase (AST) $\leq 2.5 \times$ upper limit of normal (ULN). • Total bilirubin $\leq 1.5 \times$ ULN (unless bilirubin rise is due to Gilbert's syndrome or of non-hepatic origin). • Serum creatinine $\leq 2 \times$ ULN or GFR ≥ 30 ml/min based on either the estimated Glomerular Filtration Rate (Crockcroft-Gault) or measured GFR from 24-hour urine sample. Study participants with $30 < \text{GFR} < 60$ will be treated according to manufacturer's instruction with lenalidomide 10mg rather than 25 mg. 
12. Ability to understand and willingness to sign a written informed consent from (ICF).
 
13. Ability to adhere with the study visit schedule and other protocol procedures.
 
14. A negative pregnancy test will be required for all women of child bearing potential within 7 days prior to study treatment start. Breast feeding is not permitted.
 
15. Fertility requirements
 
 • Female patients with child bearing potential must have a negative pregnancy test at least 7 days before starting treatment drugs. • Male subject must use an effective barrier method of contraception during the study and for 3 months following the last dose if sexually active with a female of childbearing potential. • Female patients must be either post-menopausal, free from menses ≥ 2 yrs, surgically sterilized, willing to use two adequate barrier methods of contraception to prevent pregnancy or agree to abstain from sexual activity starting from screening and for 90 days afterwards. • Female patients of child bearing potential must agree to comply with the fertility and pregnancy test requirements dictated by the Rev-Assist program. 
16. Willingness to provide blood and tissue samples for correlative research purposes

--	--

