 - Serum creatinine $\leq 2 \times$ ULN or GFR $\geq 30 \text{ ml/min}$ based on either the estimated Glomerular Filtration Rate (Crockcroft-Gault) or measured GFR from 24-hour urine sample. Study participants with GFR 30-50 ml/min will be treated according to manufacturer's instruction with lenalidomide 10mg rather than 25 mg.
- 11. Ability to understand and willingness to sign a written informed consent form (ICF).
- 12. Ability to adhere with the study visit schedule and other protocol procedures.
- 13. A negative pregnancy test will be required for all women of child bearing potential within 7 days prior to registration. Breast feeding is not permitted.
- 14. Fertility requirements
 - Female patients with child bearing potential must have a negative pregnancy test at least 7 days before starting treatment drugs.
 - Male subject must use an effective barrier method of contraception during the study and for 3 months following the last dose if sexually active with a female of childbearing potential.

- Female patients must be either post-menopausal, free from menses \geq 2 yrs, surgically sterilized, willing to use two adequate barrier methods of contraception to prevent pregnancy, or agree to abstain from sexual activity starting from screening and for 90 days after lenalidomide treatment
- Female patients of childbearing potential must agree to comply with the fertility and pregnancy test requirements dictated by the Rev-Assist program.

15. Willingness to provide blood and tissue samples for correlative research purposes

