6.4.2 Medications to be Used with Caution

6.4.2.1 CYP3A – Inhibitors/Inducers

Ibrutinib is metabolized primarily by CYP3A4. Concomitant use of ibrutinib and drugs that strongly or moderately inhibit CYP3A can increase ibrutinib exposure and therefore strong

CYP3A inhibitors should be avoided.

- If a strong CYP3A inhibitor (eg, ketoconazole, indinavir, nelfinavir, ritonavir, saquinavir, clarithromycin, telithromycin, itraconazole, nefazadone, cobicistat and posaconazole) must be used, reduce ibrutinib dose to 140 mg for the duration of the inhibitor use or withhold ibrutinib treatment temporarily (for 7 days or less). Subjects should be monitored for signs of ibrutinib toxicity.
- If a moderate CYP3A inhibitor (eg, voriconazole, erythromycin, amprenavir, aprepitant, atazanavir, ciprofloxacin, crizotinib, diltiazem, fluconazole, fosamprenavir, imatinib, verapamil, amiodarone, and dronedarone) is indicated, reduce ibrutinib to 140 mg for the duration of the inhibitor use.
- Avoid grapefruit and Seville oranges during ibrutinib treatment, as these contain moderate inhibitors of CYP3A (see Section 6.3.1).
- No dose adjustment is required in combination with mild inhibitors.
- Avoid concomitant use of systemic strong CYP3A inducers (eg. Carbamazepine, rifampin, phenytoin, and St. John's Wort). Consider alternative agents with less CYP3A induction.

A list of common CYP3A inhibitors and inducers is provided in Appendix II. A comprehensive list of inhibitors, inducers and substrates may be found at <http://medicine.iupui.edu/clinpharm/ddis/main-table/>.

This website is continually revised and should be checked frequently for updates.

For the most comprehensive effect of CYP3A inhibitors or inducers of ibrutinib exposure, please refer to the current version of the IB.

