8.2.1 Ibrutinib Dose Modifications for Use with CYP3A Inhibitors

The coadministration of ibrutinib with a strong or moderate CYP3A inhibitor may increase ibrutinib plasma concentrations. Increased ibrutinib concentrations may increase the risk of drug-related toxicity. Dose modifications of ibrutinib are recommended when used concomitantly with posaconazole, voriconazole and moderate CYP3A inhibitors.

Table 14 Recommended dose modifications for ibrutinib

Patient Population	Coadministered Drug	Recommended Ibrutinib Dose
B-Cell Malignancies	• Moderate CYP3A inhibitors	280 mg once daily Interrupt dose as recommended (see label)

	
• Voriconazole 200 mg twice daily• Posaconazole suspension 100 mg once daily, 100 mg twice daily, or 200 mg twice daily	140 mg once daily Interrupt dose as recommended (see label)
B-Cell Malignancies	
• Posaconazole suspension 200 mg three times daily or 400 mg twice daily• Posaconazole IV injection 300 mg once daily• Posaconazole delayed-release tablets 300 mg once daily	70 mg once daily Interrupt dose as recommended (see label)
	
• Other strong CYP3A inhibitors	Avoid concomitant use. If these inhibitors will be used short-term (such as anti-infectives for seven days or less), interrupt ibrutinib

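### Lenalidomide dosing in renal impairment and ibrutinib dosing with CYP3A inhibitors differ between sections, by 1.5- to 2.5-fold for some eligible patients

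*Combined protocol and SAP*

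**What the plan says.** **Lenalidomide and renal function.** Section 1.2 says "Patients with GFR 30-60 ml/min will receive lenalidomide 10 mg daily", with no restriction to particular dose levels. The synopsis (inclusion item 11) sets the range strictly between 30 and 60 and refers to the manufacturer's "instruction with lenalidomide 10mg rather than 25 mg". Section 3.1 (item 10) says "Study participants with GFR 30-50 ml/min will be treated according to" the manufacturer's instruction, again naming 10 mg in place of 25 mg. Tables 3 and 7 assign 15 mg at level 1 and 25 mg at levels 2 and 3.

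**Ibrutinib with a moderate CYP3A inhibitor.** Section 6.4.2.1 says that if one "is indicated, reduce ibrutinib to 140 mg for the duration of the inhibitor use". The moderate-inhibitor row of Table 14 (Section 8.2.1) says "280 mg once daily Interrupt dose as recommended". Voriconazole has its own Table 14 entry, "140 mg once daily Interrupt dose as recommended", which agrees with Section 6.4.2.1.

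**Ibrutinib with a strong CYP3A inhibitor.** If one must be used, Section 6.4.2.1 says to "reduce ibrutinib dose to 140 mg for the duration of the inhibitor use or withhold ibrutinib treatment temporarily", the hold being limited to 7 days. Table 14 says to avoid strong inhibitors other than posaconazole, and adds: "If these inhibitors will be used short-term (such as anti-infectives for seven days or less), interrupt ibrutinib". For the higher posaconazole regimens Table 14 gives 70 mg once daily.

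**The concern.** These are operative dosing instructions, and they give different answers for the same patient. The affected drugs are the two whose combination is being dose-ranged, and the MTD is the primary endpoint. The rules apply in every cycle and in the expansion cohort as well as in escalation. Two sites following different sections could give the same type of patient different doses, each in compliance with the protocol. That is a safety matter for the patient, and it blurs what was given under a nominal dose level.

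The situations are foreseeable. GFR of 30 or above is admitted by design. Moderate inhibitors are not excluded at entry, and the list in Section 6.4.2.1 includes ciprofloxacin, fluconazole, diltiazem, verapamil and amiodarone. Sections 1.4.2.3 and 1.4.2.5 name infection and atrial fibrillation as ibrutinib risks, and Section 6.4.1 permits antimicrobial prophylaxis.

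**Working it through.** The check sets the rules side by side. The only arithmetic is the ratio of the doses.

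**Step 1. Lenalidomide by GFR (ml/min).**

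| GFR | Synopsis item 11 | Section 1.2 | Section 3.1 item 10 |
|---|---|---|---|
| exactly 30 | assigned dose (strict bound) | 10 mg | 10 mg |
| above 30, up to 50 | 10 mg | 10 mg | 10 mg |
| above 50, below 60 | 10 mg | 10 mg | assigned 15 or 25 mg |
| exactly 60 | assigned dose (strict bound) | 10 mg | assigned 15 or 25 mg |

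The main conflict begins just above 50; GFR of exactly 50 is not affected.

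- Levels 2 and 3: 25 / 10 = 2.5-fold.
- Level 1: 15 / 10 = 1.5-fold.

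Naming 25 mg as the dose being replaced, as the synopsis and Section 3.1 do, does not fit level 1, where the assigned dose is 15 mg.

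**Step 2. Ibrutinib by co-medication.**

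| Co-medication | Section 6.4.2.1 | Table 14 | Result |
|---|---|---|---|
| Mild inhibitor | no adjustment | no row | no conflict |
| Moderate, other than voriconazole | 140 mg | 280 mg | conflict |
| Voriconazole | 140 mg | 140 mg | agree |
| Posaconazole, lower-dose suspension | 140 mg, or hold for up to 7 days | 140 mg | 140 mg available in both |
| Posaconazole, higher-dose suspension, IV or delayed-release tablets | 140 mg, or hold for up to 7 days | 70 mg | conflict |
| Other strong inhibitor | 140 mg, or hold for up to 7 days | avoid; interrupt if short-term | conflict |

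- Moderate inhibitor: 280 / 140 = 2-fold. Against an assigned 560 mg this is 140 / 560 = 25% or 280 / 560 = 50%. Against 840 mg it is 17% or 33%.
- Higher-dose posaconazole: 70 / 140 = half a capsule. Section 11.1.1 supplies only 140 mg capsules, and Section 6.3.1 requires them to be swallowed whole and not opened.

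**Step 3. Does anything in the protocol break the tie?**

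- Table 13's renal row covers only GFR below 30.
- Appendix II points to a Section 5.4 for CYP3A instructions, but Section 5 has no subsections.
- Table 14 is labelled for B-cell malignancies. It has no row for any other population, so the label does not take this trial's patients outside it.
- No statement gives one section precedence over another.

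**The case against.** **A tie-breaker exists.** All three renal statements defer to the manufacturer, and Section 6.3.2 lets lenalidomide be given per package insert. That does not settle the matter. The three statements cite the same authority for different ranges, and Section 6.3.2 equally allows institutional standard or investigator discretion.

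**The strong-inhibitor cases are limited by design.** This stands. Exclusion item 15 bars strong inhibitors in the 7 days before the first ibrutinib dose and bars patients who need them continuously, and Section 6.4.2.1 says to avoid them. The conflict therefore concerns only on-study use.

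**The CYP3A conflict is narrower than it looks.** A reader might infer that any patient on a CYP3A inhibitor gets a different dose depending on the section. The tables above do not support that: voriconazole and mild inhibitors are not in conflict, and lower-dose posaconazole has 140 mg available in both places.

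**The wording about 25 mg is loose rather than harmful.** This is largely fair, since Section 1.2 already applies 10 mg at every level. It still needs correcting because it can be read as exempting level 1.

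**The 3+3 tally.** A reader might go further and infer that the escalation decision itself is compromised, because the protocol defines no DLT-evaluable patient and no replacement for someone who leaves cycle 1 early without toxicity. The documents do not support that. Sections 1.2 and 7.3 count patients treated at a level, and Section 14.3.1 includes eligible, consented patients who began treatment, which points to counting such a patient. Section 7.3 also records three patients on level 2 by October 2021, so a prospective rule could reach only later patients. At level 3, a clean first three does not clear the level; at most 1 DLT in 6 is required. With all six observed, the chance of passing is (1 − p)^6 + 6p(1 − p)^5, which is 0.655 at an assumed DLT rate of 20% and 0.233 at 40%. A calculation that lets 0 of 3 clear the level would not describe it.

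**Conclusion.** The dosing rules are contradictory as written and should be harmonised. Per affected patient the size is 1.5- or 2.5-fold for lenalidomide at GFR above 50 and up to about 60, and 2-fold for ibrutinib with a moderate inhibitor other than voriconazole. For strong inhibitors other than posaconazole, one section allows 140 mg and the other gives no reduced dose. For higher-dose posaconazole, the 70 mg instruction conflicts with Section 6.4.2.1 and cannot be carried out with the capsules supplied.

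These sizes rest only on the stated doses. The documents give no frequency for any of these situations, so the number of affected patients is unknown. They also do not show which GFR bound or inhibitor dose is correct, and no direction of bias in the MTD follows from them. DLT evaluability is at most a minor and separate clarification, for any level 2 or level 3 patients still to be enrolled.

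**What to change.** 1. Use one GFR range, with the endpoints stated, in the synopsis, Section 1.2 and Section 3.1. Say that 10 mg is given instead of the assigned 15 or 25 mg.
2. Use one moderate-inhibitor dose and one strong-inhibitor rule in Section 6.4.2.1 and Table 14.
3. Replace the 70 mg row with withholding ibrutinib. State a maximum duration that reconciles the 7 days in Section 6.4.2.1 with the 28-day limit in Section 8.2.
4. Until the sponsor confirms the values, apply the cautious one: GFR bound 60; ibrutinib 140 mg with moderate inhibitors; avoid other strong inhibitors, or interrupt ibrutinib if use is short-term. Section 15.7 allows an operational memo ahead of the formal amendment.

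These are wording changes. The cost is that some patients may be under-dosed in the interim: if the less cautious value proves right, they will have had 10 mg of lenalidomide instead of 15 or 25 mg, or half the intended ibrutinib dose. A long posaconazole course could also reach the 28-day limit and end study treatment.

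If the sponsor also clarifies who counts for DLT in Section 7.3, this should be separate and prospective. DLTs in patients who start at a reduced dose should not be left out of the tally, because that would remove a toxicity seen at a lower dose from the stopping rule.
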